^a Some of the assessments referred to in this section may not be captured as data in the eCRF. They are intended to be used as safety monitoring by the treating physician. Additional testing or assessments may be performed as clinically necessary or where required by institutional or local regulations.

Table 2-4: On-study Assessments^a Cycle 3 and Beyond Maintenance (Cohort 2, 3 and 4)									
Procedure	Maintenance Therapy Nivolumab 480 mg every 4 weeks 1 cycle = 8 weeks If a dose is delayed, the procedures scheduled for that same time point should also be delayed to coincide with when that time point's dosing actually occurs.								Notes
	Day 1 Week 1	Day 1 Week 2	Day 1 Week 3	Day 1 Week 4	Day 1 Week 5	Day 1 Week 6	Day 1 Week 7	Day 1 Week 8	
Safety Assessments									
Targeted Physical Examination	X				X				To be performed only as clinically indicated within 72 hours prior to dosing
Vital Signs	X				X				Including BP, HR, and temperature
Physical Measurements (including performance status)	X				X				Weight and KPS within 72 hours prior to dosing.
Adverse Events Assessment	Continuously								
Review of Concomitant Medications	X				X				
Laboratory Tests	X				X				Within 72 hours prior to re-dosing to include CBC w/ differential, AST, ALT, ALP, T.Bili, BUN or serum urea level, creatinine. Ca, Mg, Na, K, Cl, LDH, glucose, amylase, lipase, TSH (with reflexive Free T4 and Free T3)
Pregnancy Test (WOCBP Only)	X				X				Within 24 hours prior to first dose for WOCBP only, and Q 4 weeks

Table 2-4: On-study Assessments^a Cycle 3 and Beyond Maintenance (Cohort 2, 3 and 4)										
Procedure	Maintenance Therapy Nivolumab 480 mg every 4 weeks 1 cycle = 8 weeks If a dose is delayed, the procedures scheduled for that same time point should also be delayed to coincide with when that time point's dosing actually occurs.								Notes	
	Day 1 Week 1	Day 1 Week 2	Day 1 Week 3	Day 1 Week 4	Day 1 Week 5	Day 1 Week 6	Day 1 Week 7	Day 1 Week 8		
Clinical Drug Supply										
Administer Nivolumab 480 mg	X				X					Cycle 3 dosing to begin 6 weeks ± 3 days after last dose in Cycle 2. Subsequent doses may be administered within 3 days of the scheduled date if necessary.
[REDACTED]										
[REDACTED]	■				■					[REDACTED]
[REDACTED]	■				■					[REDACTED]
[REDACTED]	■				■					

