There will be no dose escalations or reductions of nivolumab or ipilimumab allowed. For dosing cycles every 8 weeks, participants may be dosed within a ± 3 day window. Premedications are not recommended for the first dose of nivolumab.

Doses of nivolumab or ipilimumab may be interrupted, delayed, or discontinued depending on how well the participant tolerates the treatment. Dosing visits are not skipped, only delayed.

Participants should be carefully monitored for infusion reactions during nivolumab administration. If an acute infusion reaction is noted, participants should be managed according to [Section 7.4.2](#).

Nivolumab infusions are compatible with polyvinyl chloride (PVC) or polyolefin containers and infusion sets, and glass bottles.

Ipilimumab injection can be used for IV administration without dilution after transferring to a PVC, non-PVC/non-DEHP or glass container and is stable for 24 hours at 2-8°C or room temperature/room light (RT/RL). For ipilimumab storage instructions, refer to ipilimumab IB and/or pharmacy reference sheets.

Separate infusion bags and filters should be used when administering nivolumab and ipilimumab on the same day.

Ipilimumab is to be administered as a 30 minute IV infusion, using a volumetric pump with a 0.2 to 1.2 micron in-line filter at the protocol-specified dose. The drug can be diluted with 0.9% normal saline or 5% Dextrose Injection to concentrations between 1 mg/mL and 4 mg/mL. It is not to be administered as an IV push or bolus injections. Care must be taken to assure sterility of the prepared solutions, since the drug product does not contain any antimicrobial preservatives or bacteriostatic agents. At the end of the infusion, flush the line with a sufficient quantity of normal saline or 5% dextrose solution.

7.1.1 Cohort 1

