 - Grade 4 drug-related endocrinopathy adverse events, such as, hyper- or hypothyroidism, or glucose intolerance, which resolve or are adequately controlled with physiologic hormone replacement (corticosteroids, thyroid hormones) or glucose-controlling agents, respectively, may not require discontinuation after discussion with and approval from the BMS Medical Monitor.

- Any event that leads to delay in dosing lasting > 8 weeks during Cycle 1- 2, and >10 weeks in cycle 3 or later for Cohorts 2-4, and >10 weeks for Cohort 1, from the previous dose requires discontinuation, with the following exceptions:
 - Dosing delays to allow for prolonged steroid tapers to manage drug-related adverse events are allowed.
 - Dosing delays lasting longer than the number of weeks allowed for the respective cohorts that occur for non-drug-related reasons may be allowed if approved by the BMS medical monitor.

Prior to re-initiating treatment in a participant with a dosing delay lasting > 8 weeks for Cohorts 2 through 4, or >10 weeks for Cohort 1, the BMS medical monitor must be consulted and provide written approval for participants with expected clinical benefit as per investigator assessment. Tumor assessments should continue as per protocol even if dosing is delayed. Periodic study visits to assess safety and laboratory studies should also continue every 6 weeks or more frequently if clinically indicated during such dosing delays.

Any adverse event, laboratory abnormality, or intercurrent illness which, in the judgment of the Investigator, presents a substantial clinical risk to the participant with continued nivolumab dosing.

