7.4 Extent of Exposure

7.4.1 Administration of Study Therapy

The following parameters will be summarized (descriptive statistics) for all treated subjects, according to the general methods:

- Number of combined doses received (nivolumab + ipilimumab). A subject will be considered to have received combined doses of ipilimumab and nivolumab, if both infusions are administered on the same date.
- Number of doses received (nivolumab and ipilimumab)
- Cumulative dose (nivolumab and ipilimumab) in mg or mg/kg
- Relative dose intensity (%) using the following categories: < 50%; 50 - < 70%; 70 - < 90%; 90 - < 110%; ≥ 110%. (nivolumab and ipilimumab)

Table 7.4.1-1: Selection and Timing of Dose

Study Treatment	Unit Dose Strength(s)/Dosage Level(s)	Dosage Formulation Frequency of Administration	Route of Administration
Cohort 1	Nivolumab 6 mg/kg Ipilimumab 1 mg/kg Nivolumab 480 mg	Combination: D1W1 and then every 8 weeks. Monotherapy beginning D1W5 of C1, and then every 8 weeks	Nivolumab IV Ipilimumab IV
Cohort 2, 3, and 4	Nivolumab 3 mg/kg Ipilimumab 1 mg/kg Nivolumab 480 mg	Combination therapy: every 3 weeks for 4 doses. Maintenance monotherapy every 4 weeks afterwards.	Nivolumab IV Ipilimumab IV

Table 7.4.1-2: Study Therapy Parameter Definitions

	Cohort 1		Cohort 2, 3 and 4	
	Nivolumab	Ipilimumab 1 mg/kg	Nivolumab	Ipilimumab 1 mg/kg
Actual Dose (mg)	Actual dose is defined as the total dose delivered (mg) within each dosing visit.	Actual Dose (mg) is defined as the total dose delivered (mg) within each dosing visit.	Actual dose is defined as the total dose delivered (mg) within each dosing visit.	Actual Dose (mg) is defined as the total dose delivered (mg) within each dosing visit.
Actual Dose Level (mg/kg)	Actual Dose Level (mg/kg) is defined as the actual dose delivered (mg) within a dosing visit /most recent weight (kg) at the dosing visit.	Actual Dose Level (mg/kg) is defined as the actual dose delivered (mg) within a dosing visit /most recent weight (kg) at the dosing visit.	Actual Dose Level (mg/kg) is defined as the actual dose delivered (mg) within a dosing visit /most recent weight (kg) at the dosing visit.	Actual Dose Level (mg/kg) is defined as the actual dose delivered (mg) within a dosing visit /most recent weight (kg) at the dosing visit.

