Cumulative Dose (mg/Kg)	Cumulative Dose (mg/kg) is the sum of the actual dose levels administered to a subject during the study.	Cumulative Dose (mg/kg) is the sum of the actual dose levels administered to a subject during the study.	Cumulative Dose (mg/kg) is the sum of the actual dose levels administered to a subject during the study.	Cumulative Dose (mg/kg) is the sum of the actual dose levels administered to a subject during the study.
Cumulative Dose (mg)	Cumulative Dose (mg) is the sum of the actual doses administered to a subject during the study.	Cumulative Dose (mg) is the sum of the actual doses administered to a subject during the study.	Cumulative Dose (mg) is the sum of the actual doses administered to a subject during the study.	Cumulative Dose (mg) is the sum of the actual doses administered to a subject during the study.
Total Expected Dose (mg)	$[6 \times \text{Weight}^* \times (\text{Last dose date of } 6\text{mg/kg} - \text{Start dose date of } 6\text{mg/kg} + 56)/56]$ + $[480 \times (\text{Last dose date of } 480 \text{ mg} - \text{Start dose date of } 480 \text{ mg} + 56)/56]$ *Average weight during 6 mg/ kg dosing is used.	$[1 \times \text{Weight}^* \times (\text{Last dose date} - \text{Start dose date} + 56)/56]$ *Average weight during 1 mg/ kg dosing is used.	$[3 \times \text{Weight}^* \times (\text{Last dose date of } 6\text{mg/kg} - \text{Start dose date of } 6\text{mg/kg} + 21)/21]$ + $[480 \times (\text{Last dose date of } 480 \text{ mg} - \text{Start dose date of } 480 \text{ mg} + 28)/28]$ *Average weight during 3 mg/ kg dosing is used.	$[1 \times \text{Weight}^* \times (\text{Last dose date} - \text{Start dose date} + 21)/21]$ *Average weight during 1 mg/ kg dosing is used.

Table 7.4.1-2: Study Therapy Parameter Definitions

	Cohort 1		Cohort 2, 3 and 4	
	Nivolumab	Ipilimumab 1 mg/kg	Nivolumab	Ipilimumab 1 mg/kg
Relative Dose Intensity (%)	Cumulative Dose (mg) x100/ Total Expected Dose (mg)	Cumulative Dose (mg) x100/ Total Expected Dose (mg)	Cumulative Dose (mg) x100/ Total Expected Dose (mg)	Cumulative Dose (mg) x100/ Total Expected Dose (mg)
Duration of Treatment	Last dose date - Start dose date +1. Last dose date is the last date subject received Nivolumab 6 mg/kg or 480 mg.	Last dose date - Start dose date +1	Last dose date - Start dose date +1. Last dose date is the last date subject received Nivolumab 3 mg/kg or 480 mg.	Last dose date - Start dose date +1

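### In Cohorts 2–4 a late start of 480 mg maintenance does not lower nivolumab relative dose intensity, because the expected-dose term starts at the actual first 480 mg dose

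*SAP*

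**What the plan says.** SAP Table 7.4.1-2 defines RDI as "Cumulative Dose (mg) x100/ Total Expected Dose (mg"). For nivolumab in Cohorts 2–4 the expected dose is the sum of two terms:

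- Combination: "3 \times \text{Weight}^* \times (\text{Last dose date of } 6\text{mg/kg} - \text{Start dose date of } 6\text{mg/kg} + 21)/21". It closes 21 days after the last combination dose.
- Maintenance: "480 \times (\text{Last dose date of } 480 \text{ mg} - \text{Start dose date of } 480 \text{ mg} + 28)/28". It opens on the date the first 480 mg dose was actually given.

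SAP Table 7.4.1-1 gives the schedule as "Combination therapy: every 3 weeks for 4 doses. Maintenance monotherapy every 4 weeks afterwards". Protocol Table 2-4 fixes the interval between the two phases: "Cycle 3 dosing to begin 6 weeks ± 3 days after last dose in Cycle 2". Protocol 7.1.2 gives the same interval. Protocol 7.1 states "Dosing visits are not skipped, only delayed", and Protocol 7.4 permits no dose reductions, so lost intensity arises mainly through delay.

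SAP 7.4.1 reports RDI by category: "Relative dose intensity (%) using the following categories: < 50%; 50 - < 70%; 70 - < 90%; 90 - < 110%; ≥ 110"%. SAP 7.4.2.1 separately tabulates the number, length and reason of delays of 4 days or more, measured from the scheduled date.

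**The concern.** The interval between the last combination dose and the first 480 mg dose belongs to neither term. Leaving it out of both handles the planned 6-week gap correctly, but it also removes any unplanned extension of that gap. If maintenance starts late, the first and last 480 mg dates move together and the delay drops out of the denominator.

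A hold at this point is plausible. It follows the combination course, and Protocol 8.1.1 says of its delay limits: "Dosing delays to allow for prolonged steroid tapers to manage drug-related adverse events are allowed".

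What is at stake is the accuracy of one planned exposure summary. For late starters the error always runs towards higher delivered intensity. SAP 7.1 reports the cohorts separately, and two of them are planned at about 25 participants, so one participant placed in the wrong RDI category moves that category by 1/25 = 4 percentage points.

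**Working it through.** The documents state no RDI figure to reproduce, so the first check is whether the SAP formula returns 100% for a participant dosed on schedule.

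**Inputs from the documents**
- Combination doses on days 0, 21, 42 and 63.
- Planned first 480 mg dose on day 63 + 42 = 105, then every 28 days.
- Size of a plausible delay *d* at the switch: Protocol 8.1.1 sets a limit of 10 weeks from the previous dose for cycle 3 or later in Cohorts 2–4, which allows 70 − 42 = 28 days late. The re-initiation paragraph of 8.1.1, and 8.1.2, use 8 weeks for these cohorts, which allows 56 − 42 = 14 days. These passages must be reconciled; here they serve only to choose values of *d*. Exceptions permit longer delays.

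**Assumptions not in the documents**
- Weight 80 kg (range 60–100 kg), so 240 mg per combination dose.
- *n* maintenance doses, from 1 to 22.
- The dates labelled 6 mg/kg in the combination term are taken as the dates of the 3 mg/kg doses.

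**Step 1. SAP formula**
- Combination term: 240 × (63 − 0 + 21)/21 = 960 mg.
- Maintenance term, first dose on day 105 + *d*, last on day 105 + *d* + 28(*n* − 1): 480 × [28(*n* − 1) + 28]/28 = 480*n* mg. The delay has cancelled.
- Cumulative dose: 960 + 480*n* mg.
- RDI is 100% on schedule, and 100% for every *d*.

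**Step 2. Same formula, maintenance clock started at day 105**
- Maintenance term: 480 × [*d* + 28(*n* − 1) + 28]/28 = 480*n* + 480*d*/28 mg.
- A 14-day delay adds 240 mg to the expected dose; a 28-day delay adds 480 mg.

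| Maintenance doses | Cumulative dose (mg) | SAP RDI | Planned anchor, 14 days late | Planned anchor, 28 days late |
|---|---|---|---|---|
| 1 | 1,440 | 100% | 85.7% | 75.0% |
| 2 | 1,920 | 100% | 88.9% | 80.0% |
| 4 | 2,880 | 100% | 92.3% | 85.7% |
| 6 | 3,840 | 100% | 94.1% | 88.9% |
| 12 | 6,720 | 100% | 96.6% | 93.3% |
| 22 | 11,520 | 100% | 98.0% | 96.0% |

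Example: four doses, 28 days late, 2,880/(2,880 + 480) = 85.7%.

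**Step 3. When the reporting category changes**
- RDI is below 90% when 960 + 480*n* < 9 × 480*d*/28.
- For *d* = 28: 960 + 480*n* < 4,320, so *n* ≤ 6.
- For *d* = 14: 960 + 480*n* < 2,160, so *n* ≤ 2.
- At 60 kg the limits are 7 and 2 doses; at 100 kg they are 6 and 1.

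**Step 4. One 28-day delay in three positions (80 kg, six maintenance doses, SAP formula)**
- Before the fourth combination dose: expected 240 × (91 + 21)/21 + 2,880 = 4,160 mg; RDI 3,840/4,160 = 92.3%.
- Between two 480 mg doses: expected 960 + 480 × (168 + 28)/28 = 4,320 mg; RDI 88.9%.
- At the switch: expected 3,840 mg; RDI 100%.

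The formula is therefore not designed to tolerate delay in general. It misses delay at one position only.

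**The case against.** The strongest reply is that the report would still show the delay. SAP 7.4.2.1 counts it, with length and reason; SAP 7.4.1 adds a by-subject dosing listing; duration of treatment spans the gap. Number of doses and cumulative dose are unaffected. All of this stands. A reader might infer that the delay is hidden from the study report, and the documents do not support that: it is missing from RDI alone.

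A reader might also infer that the interpretation of immune-mediated event incidence is compromised. Nothing visible in either document reads that incidence against RDI. SAP 7.6.1.1 gives a number and percentage of treated participants with no exposure adjustment.

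Nor does the flaw single out everyone held for toxicity. Holds between combination doses or between 480 mg doses are counted, participants who never start 480 mg are untouched, and a late switch may have a non-drug-related cause.

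It can further be said that separate phase terms are a reasonable convention, and that Cohort 1's 480 mg term is anchored in the same way. The convention is sound, as the 100% on-schedule result shows; only the anchor fails. In Cohort 1 the two dose types alternate, so if a late first 480 mg dose pushes back the later doses, the 6 mg/kg term picks the delay up. At 80 kg with 28 days' delay and three doses of each type, expected dose is 480 × (140 + 56)/56 + 480 × (112 + 56)/56 = 3,120 mg against 2,880 mg given, or 92.3%. With only one dose of each type it would still read 100%. Cohorts 2–4 have no such alternation, so the loss there is complete.

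**Conclusion.** The expected-dose formula for nivolumab in Cohorts 2–4 is wrong as written for participants who start 480 mg late. It leaves RDI at 100% whatever the length of the switch delay, while counting the same delay elsewhere. For a 28-day delay at 80 kg the overstatement falls from 25.0 points with one maintenance dose to 4.0 points with 22.

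This is a modest, one-directional error in a descriptive exposure measure. Its effect on the reported tables cannot be estimated, because the documents do not say how often the switch is delayed. The percentages rest on the assumed weight, on on-time combination dosing, on regular 28-day dosing after the switch, and on reading the combination term's dates as those of the 3 mg/kg doses. The cancellation of the delay does not depend on the weight or on the number of maintenance doses.

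**What to change.** In SAP Table 7.4.1-2, nivolumab, Cohorts 2–4:

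1. For participants who received all four combination doses, replace the start date in the 480 mg expected-dose term with last combination dose date + 42 days, the start already planned in the protocol.
2. For participants moved early to monotherapy (Protocol 5.1 and 8.1.2), who have no planned start date, keep the actual date, flag them in the table, and footnote that their RDI does not reflect any delay at the switch. This leaves a known gap in that group but makes it visible.
3. Reconcile the 6 mg/kg dates in the combination term with the 3 mg/kg level stated for these cohorts. The cell cannot be programmed as printed.

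The cost is one formula, one footnote and the matching programming; no new data are needed. Some reported RDI values become less favourable. Starts within the ±3-day window will also move RDI slightly: at 80 kg with one maintenance dose, 3 days late gives 1,440/(1,440 + 480 × 3/28) = 96.6%, which stays in the 90 to <110% category.

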7.4.2 Modifications of Study Therapy

7.4.2.1 Dose Delays

A dose will be considered as actually delayed if the delay is exceeding 3 days (i.e., greater than or equal to 4 days from scheduled dosing date). Dose delays will be divided into following categories: 4-7 days, 8-14 days, 15-42 days, >42 days. Reason for dose delay will be retrieved from CRF dosing pages.

The following parameters will be summarized:

- Number of dose delays per subject, length of delay and reason for dose delay
- Number of subjects with at least one dose delay along with reason for dose delay.

7.4.2.2 Dose Reductions/Escalations and Infusion Interruption

There will be no dose escalations or reductions of nivolumab or ipilimumab allowed per protocol. Nivolumab or ipilimumab infusion can be interrupted and/or the IV infusion rate can be reduced. This information will be retrieved from CRF dosing pages.

The following parameters will be summarized for nivolumab and ipilimumab administration by cohorts:

- Number of subjects with at least one dose infusion interrupted along with the reason of all interruptions,
- Number of subjects with at least one infusion with IV rate reduced along with the reason of all rate reductions.

A by subject listing of study drug administered will be provided.

7.5 Efficacy

7.5.1 Secondary Analyses

7.5.1.1 Progression-Free Survival 1

PFS 1 will be summarized by the KM product-limit method for all treated subjects for all cohorts and all intermediate/poor risk subjects and all favorable risk subjects only for Cohort 1. Median values of PFS 1, along with two-sided 95% CI using the Brookmeyer and Crowley method, will be calculated. Standard error will be calculated using the Greenwood formula. Survival rate at different time points (at 6, 12, 18, 24 months) will be estimated based on KM method for all treated subjects for all Cohorts and all intermediate/poor risk subjects and all favorable risk subjects only for Cohort 1.

PFS 1 will be graphically displayed along with the median and 95% CI. The source of progression (death versus progression) will be summarized by cohort for all Treated subjects and all intermediate/poor risk subjects and all favorable risk subjects only for Cohort 1.

7.5.1.2 Objective Response Rate and Clinical Benefit Rate

The Objective Response Rate (ORR) and Clinical Benefit Rate (CBR) will be summarized by binomial response rates and their corresponding two-sided 95% exact CIs using the Clopper-Pearson method. This analysis will be performed for all response evaluable subjects for all cohorts and response evaluable intermediate/poor risk subjects and all response evaluable favorable risk subjects will be presented only for Cohort 1. The BOR will be tabulated.

Listings of BOR, per time point tumor response, and lesion evaluations will be provided.

7.5.1.3 Time to Response

TTR will be summarized using the KM method for all response evaluable subjects for all cohorts, all intermediate/poor risk subjects and all favorable risk subjects only for Cohort 1. Median values

of TTR, along with two-sided 95% confidence intervals using the Brookmeyer and Crowley method, will also be calculated.

TTR will be graphically displayed using the cumulative rate of response over time.

[figure not shown]

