10.3.1 Efficacy Analyses

Endpoint	Statistical Analysis Methods
Primary	Not applicable

Endpoint	Statistical Analysis Methods
Secondary	
PFS will be summarized by KM product-limit method for all treated participants and all response evaluable participants, respectively. Median values of PFS, along with two-sided 95% CI using Brookmeyer and Crowley method, will be calculated. Associated two-sided 95% CIs will be calculated using the Greenwood formula. This analysis will be performed for all treated participants and for all response evaluable participants for both PFS 1 as secondary endpoint and PFS 2 as exploratory endpoint.
 
The ORR will be summarized by binomial response rates and their corresponding two-sided 95% exact CIs using the Clopper-Pearson method. This analysis will be performed for all response evaluable participants.
 
Time to response (TTR) is analyzed using the KM methodology, for all evaluable participants. KM curve was to represent the cumulative rate of response over time. For the non-responders, time to response was censored at the maximum time of response + 1 day of all participants in their respective treatment group.
 
The assessed DOR will be summarized for all response evaluable participants who achieve confirmed PR or CR using the Kaplan-Meier (KM) product-limit method. Median values of DOR, along with two-sided 95% CI using Brookmeyer and Crowley method, will also be calculated. In addition, the percentage of responders still in response at different time points (3, 6, 12, 18, and 24 months and at end of study) will be presented based on the DOR KM plot. This analysis will be performed for all response evaluable participants who achieve confirmed PR or CR.

[REDACTED]	[REDACTED]

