Death without progression and without subsequent anti-cancer therapy	Date of death	Progressed

3. **ORR:** ORR is defined as the number of subjects with a best overall response (BOR) of CR or PR divided by the number of response evaluable subjects. BOR is defined as the best response designation, as determined by the investigator, recorded between the date of first dose and the date of objectively documented progression (per RECIST 1.1 or Clinical) or the date of subsequent therapy, whichever occurs first. For subjects without documented progression or subsequent therapy, all available response designations will contribute to the BOR determination. For subjects who continue treatment beyond progression, the BOR should be determined based on response designations recorded up to the time of the initial RECIST 1.1 defined PD or clinical progression, whichever occurs first.
4. **TTR:** TTR is defined as time from the date of first dose to first documented CR or PR. Cohort 1 subjects who do not have a CR or PR will be censored at the maximum time of response + 1 day. Subjects who do not have a CR or PR in combined cohort 2, 3 and 4 will be censored at the maximum time of response in combined cohort +1 day.
5. **DOR:** DOR will be computed for subjects who achieve PR or CR only. The DOR is defined as the time between the date of first confirmed response to the date of the first documented tumor progression (per RECIST 1.1), or death due to any cause, whichever occurs first. Subjects who neither progress nor die will be censored on the date of their last evaluable tumor assessment. Subjects who received any subsequent anti-cancer therapy on or after the

date of first confirmed response will be censored at the last evaluable tumor assessment prior to or on the date of initiation of the subsequent anti-cancer therapy.

[REDACTED]

[REDACTED]

[REDACTED]

[REDACTED]

[REDACTED]

[REDACTED]

[REDACTED]

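### The planned Kaplan-Meier median for time to response depends on how many respond as well as how fast, so it should not be reported or compared as the median time to response

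*SAP*

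**What the plan says.** TTR is a named secondary endpoint. SAP 4.2 gives the definition: "TTR is defined as time from the date of first dose to first documented CR or PR". For subjects without a response it says "Cohort 1 subjects who do not have a CR or PR will be censored at the maximum time of response + 1 day", and non-responders "in combined cohort 2, 3 and 4 will be censored at the maximum time of response in combined cohort +1 day". Protocol 10.3.1 has the same rule by treatment group: "For the non-responders, time to response was censored at the maximum time of response + 1 day of all participants in their respective treatment group".

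On the analysis, SAP 7.5.1.3 says "TTR will be summarized using the KM method for all response evaluable subjects for all cohorts", and also for the intermediate/poor and favorable risk groups of Cohort 1. It then asks for median values "of TTR, along with two-sided 95% confidence intervals using the Brookmeyer and Crowley method, will also be calculated". Protocol 10.3.1 states what the curve is for: "KM curve was to represent the cumulative rate of response over time". SAP 7.5.1.3 also plans the plot as a cumulative response display.

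SAP 7.1 reports the four cohorts separately. It offers Kaplan-Meier medians where appropriate, but its list of time-to-event endpoints does not name TTR, and SAP 7.5.1.3 requests the TTR median without condition. The only responder-level TTR output in the visible text is a by-subject listing, in SAP 7.5.1.4.

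**The concern.** A reader of a table row called median TTR will take it as the typical wait until response among those who respond. The planned statistic answers a different question: when had half of everyone evaluable responded? That answer combines the response rate with the speed of response.

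Two consequences follow. In a cohort where fewer than half respond, the row reads as not reached and says nothing about speed. Where more than half respond, two cohorts or two risk groups with identical response times among responders can show different medians simply because their response rates differ, and the difference could be read as slower response. The SAP produces this figure for four cohorts and for two risk groups within Cohort 1, so such side-by-side reading is likely.

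**Working it through.** **Inputs from the documents.** Analysis set: response evaluable subjects (SAP 7.5.1.3), which is also the ORR denominator (SAP 4.2). Censoring: one day after the latest response (SAP 4.2; protocol 10.3.1). Scans: weeks 12, 20, 28, 36 and so on (protocol Section 2). Planned treated numbers: 100, 50, 25 and 25 (SAP 2.1). The documents give no TTR figure to reproduce and no expected response rate, so the rate is varied below. *Response rate* here means the share of evaluable subjects with a response counted in TTR.

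**Step 1: shape of the curve.** No one is censored before the last response in the group, so the risk set shrinks only through responses. With p the response rate and F(t) the share of responders who have responded by time t:

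S(t) = 1 − p × F(t), with minimum 1 − p.

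The minimum is 0.80, 0.70, 0.60, 0.52 and 0.48 at p = 20%, 30%, 40%, 48% and 52%. Censoring Cohorts 2 to 4 at their combined maximum changes nothing, because that date is never before a cohort's own last response. The same holds for the risk groups within Cohort 1.

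**Step 2: the median.** It needs p × F(t) = 0.5, so F(t) = 0.5/p. If p is below 0.5 there is no solution. At exactly 0.5 the result depends on the software's convention. Above 0.5:

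| p | 0.5/p | Responders' percentile |
|---|---|---|
| 55% | 0.909 | 91st |
| 60% | 0.833 | 83rd |
| 70% | 0.714 | 71st |
| 80% | 0.625 | 62.5th |

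The two medians are the same quantity only at p = 100%.

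**Step 3: illustration with speed held fixed.** Assume that 60%, 20%, 10%, 6% and 4% of responders first respond at weeks 12, 20, 28, 36 and 44, so F = 0.60, 0.80, 0.90, 0.96 and 1.00. The responders' median is week 12 at every p. The planned median is:

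- p = 48%: p × F ends at 0.48; not reached.
- p = 60%: 0.36, 0.48, 0.54; week 28.
- p = 70%: 0.42, 0.56; week 20.
- p = 80%: 0.48, 0.64; week 20.

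Groups at 60% and 70% would therefore differ by 28 − 20 = 8 weeks with no difference in speed.

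**Step 4: where the two coincide.** At p = 70% with 80% of responders at week 12, p × F = 0.70 × 0.80 = 0.56 at the first scan, so both medians are week 12. When the Step 3 response dates were instead spread at random within the ±1-week scan window (simulated at n = 25, 50 and 100), the planned median exceeded the responders' median by on average about 23–28 weeks at p = 52%, 12–14 at 60%, 5–8 at 70% and 3–5 at 80%. Exact equality occurred in at most 1% of simulated cohorts.

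**Step 5: chance that the median is not reached.** This is the binomial probability that fewer than half respond, taking all treated subjects as evaluable:

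| True rate | n = 25 | n = 50 | n = 100 |
|---|---|---|---|
| 30% | 98% | 99.8% | >99.9% |
| 40% | 85% | 90% | 97% |
| 50% | 50% | 44% | 46% |
| 60% | 15% | 6% | 2% |

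**The case against.** The strongest reply is that the quantity is deliberate. Protocol 10.3.1 says the curve shows cumulative response. The time by which half of evaluable subjects have responded is a legitimate quantity, and not reached is then a valid result meaning that fewer than half responded. ORR with an exact interval is reported in the same set, so a careful reader can separate the two components. All of that stands for the curve. It does not stand for a median presented under the name TTR with no responder-only summary beside it.

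The consequence is also limited. This is an open-label safety study with descriptive efficacy analyses, and no visible test or decision uses median TTR. The by-subject listing holds the responders' times. Table content is deferred to a Data Presentation Plan that is not available here, and redacted text could hold another summary. These points lower the stakes but do not supply the missing summary.

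A reader might also infer that TTR and DOR describe different responders, because TTR runs to the first documented response and DOR starts at the first confirmed one. The documents do not support that as an error: protocol Appendix 4 (3.3.3 and 3.3.4) requires confirmation before CR or PR is assigned, so documented can reasonably be read as confirmed. The wording should still be settled. If unconfirmed responses were counted, 45% confirmed plus 8% unconfirmed would bring the curve to 1 − 0.53 = 0.47, and the median would be reached despite a confirmed ORR below 50%.

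**Conclusion.** The point holds as a matter of what the planned median estimates. It is the responders' 0.5/(response rate) quantile when at least half respond, and is not reached when fewer than half do. It should not be presented, or compared across cohorts or risk groups, as the median time to response. The result follows from the SAP's censoring rule alone; the week figures rest on an assumed spread of responses over scans, and the probabilities on assumed response rates.

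Two stronger readings go too far. One is that the planned median must differ in value from the responders' median whenever some subjects do not respond: on discrete scans the two can coincide, and at an 80% response rate the simulated gap is only 3–5 weeks, less than one 8-week scan interval. The other is that the figure will be missing in this trial: with no planning response rate in the documents, that cannot be determined. The matter is worth correcting because a named secondary endpoint is affected and the correction is nearly free. It does not touch the primary safety analysis.

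**What to change.** In SAP 7.5.1.3:

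- Add median, quartiles and range of TTR among confirmed responders, by cohort and by Cohort 1 risk group, as the TTR summary.
- Keep the all-evaluable Kaplan-Meier curve as a cumulative response plot. Either drop its median and interval, or label them as the time by which half of evaluable subjects have responded.

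In SAP 4.2, as a clarification only, state that TTR and DOR use the same confirmed responders and the same response date.

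The cost is SAP wording and one extra descriptive table. No new data are needed.
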